6.4. Interim Analyses

No interim analysis is planned for this trial.

6.5. Stopping Rules

Given the minimal risk nature of the trial, no pre-specified stopping rules are defined. The Data and Safety Monitoring Board (DSMB) meets every nine months to review safety and efficacy data and retains the authority to recommend early termination if unanticipated safety concerns arise.

6.6. Protocol Deviations

Protocol deviations are defined as any noncompliance with the study protocol. The impact of protocol deviations on the primary analysis will be evaluated through a per protocol and a complier average causal effect (CACE) analysis, described in Section 7.7.

6.7. Participant Withdrawal

Participants may withdraw from the trial at any time. Upon withdrawal, self-reported data are excluded from analysis unless the participant consents to their continued use. The primary analysis uses an intention-to-treat approach and includes all randomized physicians regardless of their degree of participation, provided they filed Medicare claims during the follow-up period, and did not ask for withdrawal.

7. STATISTICAL ANALYSIS PLAN

7.1. Statistical Objectives

The primary statistical objective is to determine whether physicians randomized to *Night Shift 2024* under-triage a smaller proportion of severely injured older patients compared to those receiving usual education, as assessed using Medicare claims data over the one-year post-

enrollment period. Secondary objectives are to evaluate the effect of the intervention on patient outcomes (30-day mortality and readmissions, functional dependence) and to assess safety (over-triage).

Exploratory objectives include evaluating: 1) the heterogeneity of treatment effect across pre-specified physician-level subgroups; 2) the mediation of the intervention's effect by dose, time between game usage and treatment of patient, and fidelity of intervention receipt; 3) the mediation of clinical outcomes by the intervention

Protocol Deviation (Version 1.3 and 1.5): We did not assess the effect of the game on functional dependence, mediation by fidelity of intervention receipt, or mediation by the game.

7.2. Sample Size

Based on prior studies, we assume that $\geq 75\%$ of enrolled physicians will encounter at least one eligible patient (i.e., enrolled in Medicare Fee-for-Service, severely injured, age ≥ 65 years), with a median number of patients per physician of 1-2. In this clustered randomization trial, physicians serve as the randomization unit. Based on data from a prior study, we assume an intraclass correlation coefficient (ICC) of 0.45, indicating the correlation in outcomes within the same physician. Under these assumptions, with 400 physicians per group ($N=800$), we can detect between a 7.4–10% difference in under-triage between the intervention and control groups with 80% power and a significance level of 0.05, using a one-sided hypothesis test. We have chosen a one-sided hypothesis test to boost statistical efficiency and because we prioritize identification of a positive effect of the intervention. A negative effect would produce the same outcome as a null: the decision to pause further efforts to disseminate the intervention.

The sample size estimate is conservative, as it is based on a simple comparison of proportions. The mixed-effects model used in the primary analysis is expected to yield greater effective power by accounting for additional sources of variance. Sample size calculations were performed using PASS 2023.

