**\* Identify the subgroups and provide a justification:**

We are studying physicians and other care providers (ED/Trauma directors) who treat or care for an adult patient population.

**8. Describe the power analysis used and cite your method of statistical analysis. If a power analysis is not possible, thoroughly justify the sample size required for the study, including appropriate literature citation (alternatively provide page reference in attached protocol):**

Based on prior studies, we assume that we can link  $\geq 75\%$  of trial participants to their National Provider Identifiers (NPIs), allowing us to link trial data to claims records, that each physician will evaluate a median of 1-2 eligible patients in the trial period, and that the intraclass correlation coefficient is 0.45. Under these assumptions, with 400 physicians per group ( $N=800$ ), we can detect between a 7.4–10% difference in under-triage between the intervention and control groups with 80% power and a significance level of 0.05, using a one-sided hypothesis test. We have chosen a one-sided hypothesis test to boost statistical efficiency and because we prioritize identification of a positive effect of the intervention. A negative effect would produce the same outcome as a null: the decision not to proceed with a Phase IV trial. Parameters for the various quantities included in our primary analysis are quite uncertain, making precise sample size simulation impossible. This difference was estimated using a simple comparison of proportions and is thus conservative. By adjusting for multiple sources of variance in our final analysis, our actual power is expected to be greater.

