		5.2.1	Secondary outcome measure of functional independence delayed	Cost of data purchase
1.4	9/29/25	7.5	Primary analysis will not include baseline covariates or random effects for the hospital	Parsimony; model stability
		7.7	Add a complier average causal effect analysis (CACE) to per protocol analysis to test the effect of study protocol compliance	Robustness
		7.10	One-sided alpha changed to a two-sided test	Improve rigor of interpretation
DATA LOCK OCCURS – October 1, 2025				
1.5	10/3/25	5.3	Re-defined dose as game usage during each intervention period instead of based on time spent.	Improve understanding of mediation
		7.1	Remove exploratory analysis of fidelity of intervention receipt; remove mediation analysis of clinical outcomes	Inability to acquire correct statistical package on CMS Virtual Desktop; results preclude necessity

SUMMARY

Study Population: The primary study population consists of 800 board-certified emergency physicians employed at non-trauma centers in the continental US. Outcomes are assessed using Medicare claims from patients aged 65 or older treated by trial physicians during the one-year post-enrollment period.

Design: This is a Phase 3, Type 1 hybrid effectiveness-implementation randomized clinical trial in which physicians are randomized 1:1 to play *Night Shift 2024* (game-based training) or to receive usual education (control). The primary outcome is assessed using Medicare claims data collected for 13 months after the close of enrollment.

Sample Size: A total of 800 physicians (400 per arm) provides 80% power to detect a 7.4% to 10% absolute reduction in under-triage at a one-sided significance level of 0.05, assuming an intraclass correlation coefficient of 0.45 and a median of 1-2 eligible patients per physician.

TABLE OF CONTENTS

1. ABBREVIATIONS	7
2. BACKGROUND AND RATIONALE	8
3. ENROLLMENT CRITERIA	8
3.1. Physician Participants	8
3.1.1. Inclusion criteria	9
3.1.2. Exclusion criteria	9
3.2. Patient Participants	9
3.2.1. Inclusion criteria	9
3.2.2. Exclusion criteria (primary analysis)	9
3.3. Hospital Characteristics	9
3.4. Key Decision Makers	10
3.4.1. Inclusion criteria (must meet at least one of the following)	10
3.4.2. Exclusion criteria	10
4. INTERVENTIONS	10
4.1. Intervention Arm (Game-Based Training)	10
4.1.1. Dosing and administration	10
4.1.2. Measurement of fidelity of treatment delivery	11
4.1.3. Measurement of fidelity of treatment receipt	11
4.2. Control Arm (Usual Education)	11

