3.2.2. Exclusion criteria (primary analysis)

- Severe injury (ISS ≥ 16) with death on the day of admission.

Protocol Deviation (Versions 1.3 and 1.2): We did not obtain Medicare Advantage claims, and so changed our inclusion criteria to patients 65 years or older with Medicare Fee-for-Service only. We also included patients treated in the 365 days after enrollment, given delays in meeting our sample size target. Finally, we included patients who presented to Level 3–5 trauma centers initially (as discussed above).

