The primary model will the following baseline covariates: patient-level characteristics (age, sex, age-adjusted Charlson Comorbidity Index score); physician-level characteristics (sex, years of experience, number of shifts per month; and hospital-level characteristics (resource availability, bed size, teaching status). The analysis is conducted on the ITT population. A one-sided hypothesis test is used at a significance level of 0.05.

The test statistic follows a chi-square distribution with degrees of freedom equal to the number of variance parameters removed. Variance components for both random effects, including estimated variances and corresponding intraclass correlation coefficients at the physician and hospital levels will be reported. These results are interpreted as evidence of the degree of clustering of patients within physicians and physicians within hospitals, respectively, and provide empirical justification for the multilevel modeling approach used in this trial.

Protocol Deviation (Version 1.4): We decided to use unadjusted primary model with no baseline covariate adjustment and clustering only at the physician level to ensure transparency and to maximize chances for model stability. In sensitivity analyses we did test the effect of

clustering at the hospital level (patients nested within patients within hospitals), and then assessed variance to determine whether to retain the clustering or not.

Protocol Deviation (Version 1.5): We had pre-specified the use of a one-sided significance test of 0.05. However, during analysis, consistent with the CONSORT guidelines, we used a two-sided test, which corresponds to a one-sided test of 0.025. We disclose this deviation in the Methods of the paper.

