7.10. Type I Error Rate

A one-sided significance level of 0.05 is used for the primary hypothesis test to boost statistical efficiency and because we prioritize identification of a positive effect of the intervention. A negative effect would produce the same outcome as a null: the decision to pause further efforts to disseminate the intervention.

Protocol deviation (Version 1.4): After database lock and prior to unmasking, the study statistician determined that a two-sided test at $\alpha = 0.05$ was more appropriate given the standard implementation of the mixed effects logistic regression framework used and CONSORT reporting requirements. This is equivalent to a one-sided threshold of $\alpha = 0.025$ and represents a more conservative standard. This deviation is disclosed in the manuscript Limitations.

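### The 80% power stated for a 7.4–10 point difference belongs to a one-sided 0.05 test. The primary test is now two-sided 0.05, which turns that statement into about 70%, and the SAP does not say so.

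*SAP*

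**What the plan says.** **Power statement.** SAP 7.2 gives a detectable difference of 7.4–10 points "with 80% power and a significance level of 0.05, using a one-sided hypothesis test". The Summary says that 800 physicians "provides 80% power to detect a 7.4% to 10% absolute reduction in under-triage at a one-sided significance level of 0.05". The Protocol (Study Design, item 8) gives the same range, power and one-sided level. Section 7.2 adds that the estimate is conservative because the mixed model should bring extra power.

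**Test used.** The revision table lists, under version 1.4 and section 7.10, "One-sided alpha changed to a two-sided test". The deviation note in 7.5 reads "we used a two-sided test, which corresponds to a one-sided test of 0.025". The note in 7.10 says that the change "represents a more conservative standard". The Appendix table also records two-sided testing.

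**Primary model.** Under version 1.4 the primary model has no baseline covariates and clusters by physician only (7.5, deviation note).

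**Inputs.** The Protocol's figure of at least 75% is the share that can be linked: "of trial participants to their National Provider Identifiers (NPIs), allowing us to link trial data to claims records". In SAP 7.2 the same figure is the share "of enrolled physicians will encounter at least one eligible patient (i.e., enrolled in Medicare Fee-for-Service, severely injured", aged 65 or over. The deviation note in SAP 3.2.2 records that the team "changed our inclusion criteria to patients 65 years or older with Medicare Fee-for-Service only". The 75%, the median of 1–2 patients, the ICC of 0.45 and the 7.4–10% are the same in both documents.

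**The concern.** The power claim is attached to a test that is no longer the primary test. Most sections affected by an amendment carry a deviation note. Section 7.2 carries none and still argues for one-sided testing. A reader who takes 80% power from the Summary and the two-sided test from 7.5 or 7.10 will put together two things that do not belong together.

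What is at stake is how a null result is read. At the stated differences the chance of missing a real effect is about 30% on the plan's own terms, not 20%. The SAP was reconstructed after the trial was complete, in response to peer review, so readers are likely to consult 7.2 when they judge the findings.

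**Working it through.** **Inputs.** From SAP 7.2: 400 physicians per arm, at least 75% contributing (so 300 to 400 per arm), 1–2 patients per physician, ICC 0.45, one-sided 0.05, 80% power, detectable difference 7.4–10 points. The control under-triage rate is not given in 7.2. SAP section 2 gives about 50% for all patients at non-trauma centers and more than 80% for those over 65. A range is therefore used below, as an assumption.

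**Step 1: reproduce the plan's figure.** Effective patients per arm = K × m / (1 + (m − 1) × 0.45).

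- Best case, K = 400 and m = 2: 800 / 1.45 = 551.7.
- Worst case, K = 300 and m = 1: 300.

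Power from a pooled two-proportion z test without continuity correction:

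| Assumed control rate | Case | Difference | One-sided 0.05 | Two-sided 0.05 |
|---|---|---|---|---|
| 50% | best | 7.4 | 79.5% | 69.4% |
| 50% | worst | 10 | 79.4% | 69.3% |
| 55% | best | 7.4 | 79.3% | 69.2% |
| 55% | worst | 10 | 79.1% | 68.9% |
| 60% | best | 7.4 | 79.8% | 69.8% |
| 60% | worst | 10 | 79.4% | 69.3% |
| 65% | best | 7.4 | 81.1% | 71.4% |
| 65% | worst | 10 | 80.5% | 70.6% |

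With a control rate of 50–65%, the plan's 80% one-sided reproduces at both ends of its range.

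**Step 2: change only the critical value.** If power is 80% at one-sided 0.05, the standardised effect is 1.645 + 0.842 = 2.486 (unrounded quantiles). Against the two-sided critical value:

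Power = Φ(2.486 − 1.960) = Φ(0.526) = 0.701.

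The control rate, ICC and cluster size do not enter this step, so under the normal approximation it holds whatever they are.

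**Step 3: detectable difference at 80% power, two-sided.** The ratio is (1.960 + 0.842) / (1.645 + 0.842) = 2.802 / 2.486 = 1.127.

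- 7.4 × 1.127 = 8.3 points.
- 10 × 1.127 = 11.3 points.

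Keeping 80% power at 7.4–10 points would have needed 1.127² = 1.27 times the sample, about 1,016 physicians instead of 800.

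**Step 4: how far the result depends on the control rate.** Differences detectable with 80% power, best to worst case:

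| Assumed control rate | One-sided 0.05 | Two-sided 0.05 |
|---|---|---|
| 50% | 7.5–10.1 | 8.4–11.3 |
| 78% | 6.5–8.9 | 7.4–10.1 |
| 80% | 6.3–8.7 | 7.2–9.9 |

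The stated range can therefore also be matched by a two-sided test if the control rate is near 78%. At 80%, two-sided power is 82.5% at 7.4 points (best case) and 80.9% at 10 points (worst case). The documents call their calculation one-sided, so Step 2 is the right correction of what they state. The true power at a given difference cannot be settled without the control rate.

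**The case against.** **The change is disclosed and stricter.** This stands. It is in the revision table, 7.5, 7.10 and the Appendix, and type I error is not inflated. Nowhere do the documents claim 80% power for a two-sided test, and nowhere do they say that a null result would exclude 7.4–10 points. The defect is a power statement left without a note.

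**The range might fit a two-sided test.** This stands in part. A reader might infer that 7.4–10 points can come only from a one-sided calculation, or that the trial as run is underpowered. Step 4 shows that neither follows, and section 2 puts under-triage above 80% in patients over 65. What remains is that the text labels the calculation one-sided, and the unstated control rate leaves the reader unable to check it.

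**Section 7.2 already allows for extra power.** This does not stand as an offset. The gain was expected from a model that accounts for further sources of variance, and version 1.4 took out the covariates and the hospital random effect.

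**Loss of Medicare Advantage patients.** A reader might infer that dropping them pushes the detectable difference well above 11 points. The documents do not support a figure. SAP 7.2 already defines its 75% on fee-for-service patients, and neither the fee-for-service share nor the distribution of patients per physician is given. A fair question does remain: the Protocol's source population included Advantage, yet its numbers are identical.

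**Section 7.2 is the planning record.** This stands. It documents why 800 physicians were chosen and should not be overwritten.

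**Conclusion.** The power statement in SAP 7.2 and the Summary does not match the primary test. On the plan's own terms, power at 7.4–10 points is about 70% rather than 80%, and the differences detectable with 80% power are about 8.3–11.3 points. This rests on the normal approximation and on accepting the one-sided 80% as stated. It is a correction of that figure and not an estimate of achieved power.

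The two meanings of the 75% are a separate inconsistency. It has no bearing on the 70%, but it belongs in the same note because it concerns the inputs to the same calculation. No estimate, confidence interval, population or test changes. This is a reporting correction of modest weight.

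**What to change.** Leave the planning paragraph as it is and add a deviation note to SAP 7.2 and the Summary that:

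1. says the 80% applies to the one-sided 0.05 test, and that under the two-sided 0.05 test the same calculation gives about 70% power at 7.4–10 points, or 80% power at about 8.3–11.3 points;
2. states the control under-triage rate used in the calculation (if it proves that the range was computed another way, report that instead);
3. says that the gain expected from the mixed model is no longer relied on, given the version 1.4 model;
4. gives the 75% one meaning, or explains why the Protocol and SAP differ, and says whether the 75% and the 1–2 patients were set on the fee-for-service pool.

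In the manuscript, read any null result from the 95% confidence interval, not from the 7.4–10 point target. Power should not be recomputed from the realised counts, since the interval already carries that information.

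The cost is a few sentences and a look at the sample-size file. No analysis is rerun. The stated power becomes less favourable unless the control rate shows otherwise.

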7.3. Analysis Populations

7.3.1. Intention-to-treat population

The intention-to-treat (ITT) population includes all randomized physicians, regardless of their adherence to the intervention, who filed at least one Medicare claim during the follow-up period and who did not ask to have their data withdrawn from the trial. This is the primary analysis population.

7.3.2. Per-protocol population

The per-protocol (PP) population includes only those physicians in the intervention arm who completed at least 2 hours of gameplay, and all physicians in the control arm who completed study tasks. The PP analysis is a pre-specified sensitivity analysis to assess the robustness of the primary findings.

7.3.3. Implementation analysis population

The implementation analysis population includes all key decision makers and trial physician participants who completed at least one semi-structured interview. No formal statistical comparisons are made in this population.

7.4. General Analytic Principles

All quantitative analyses are conducted using Stata 17.0 (StataCorp, TX). Baseline characteristics of physician participants are summarized descriptively by arm, using means and standard deviations for continuous variables and frequencies and proportions for categorical variables. No inferential statistics are used to compare baseline characteristics between arms. Patient-level and hospital-level variables are summarized similarly. Patterns of missingness are described prior to analysis to identify variables with non-random or high ($\geq 10\%$) missingness.

7.5. Primary Endpoint Analysis

The primary endpoint (under-triage) is analyzed using a generalized linear mixed model (GLMM) with a binomial error distribution, a logit link function, and an exchangeable correlation structure. The outcome is modeled at the patient level. The fixed effect is treatment arm (game-based training vs. usual education). Random effects are included at the physician and hospital levels to account for clustering of patients within physicians and physicians within hospitals. Random effects are specified as random intercepts only, with an assumption of no covariance between the physician-level and hospital-level random intercepts. This specification was selected as the most parsimonious structure consistent with the nested clustering of patients within physicians and physicians within hospitals, and to minimize the risk of convergence failure given the number of hospital-level clusters in the trial. A random intercepts-only specification is appropriate given that the primary quantity of interest is the fixed treatment effect, and there is no a priori expectation that the treatment effect varies across physicians or hospitals in a way that requires random slopes. If the model does not converge (due to the scarcity of cases within hospitals), we will remove the hospital-level random effect preferentially.

Model estimation is performed in Stata 17.0 using the melogit command adaptive Gauss-Hermite quadrature with the `intpoints(7)` option. Convergence is assessed using the following diagnostics: (1) the final convergence code, which should indicate successful convergence (code = 0 in Stata or equivalent); (2) the number of iterations required to reach convergence; and (3) the scaled gradient at convergence, which should fall below the conventional threshold of 0.001. If convergence is not achieved with the default optimizer and settings, the following pre-specified remediation steps are taken in sequence: (a) increase the number of integration points using the `intpoints()` option; and (b) rescale continuous covariates to have mean 0 and standard deviation 1.

The primary model will the following baseline covariates: patient-level characteristics (age, sex, age-adjusted Charlson Comorbidity Index score); physician-level characteristics (sex, years of experience, number of shifts per month; and hospital-level characteristics (resource availability, bed size, teaching status). The analysis is conducted on the ITT population. A one-sided hypothesis test is used at a significance level of 0.05.

The test statistic follows a chi-square distribution with degrees of freedom equal to the number of variance parameters removed. Variance components for both random effects, including estimated variances and corresponding intraclass correlation coefficients at the physician and hospital levels will be reported. These results are interpreted as evidence of the degree of clustering of patients within physicians and physicians within hospitals, respectively, and provide empirical justification for the multilevel modeling approach used in this trial.

Protocol Deviation (Version 1.4): We decided to use unadjusted primary model with no baseline covariate adjustment and clustering only at the physician level to ensure transparency and to maximize chances for model stability. In sensitivity analyses we did test the effect of

clustering at the hospital level (patients nested within patients within hospitals), and then assessed variance to determine whether to retain the clustering or not.

Protocol Deviation (Version 1.5): We had pre-specified the use of a one-sided significance test of 0.05. However, during analysis, consistent with the CONSORT guidelines, we used a two-sided test, which corresponds to a one-sided test of 0.025. We disclose this deviation in the Methods of the paper.

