**5. List the inclusion criteria:**

Intervention/Control: We plan to recruit board-certified physicians who work exclusively in the EDs of non-trauma centers in the US, and who triage adult trauma patients as part of their practice.

Interviews:

-ED directors at non-trauma centers, trauma directors at Level I/II trauma centers, first responders (paramedics)

-Patients (65 and older) and/or surrogates who were recently treated at a non-trauma center for a traumatic injury using Pitt+Me

Medicare beneficiaries (65 and older) who were treated by study physicians, with an Inpatient or Outpatient claim filed between 2023-2024 in which one of the discharge diagnoses is associated with a moderate to severe injury. We will provide ResDac with a validated crosswalk between ICD10-CM diagnoses codes and the severity of injury to identify the relevant patients.

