**6. List the exclusion criteria:**

We plan to exclude non-physician healthcare professionals (e.g., nurse practitioners, physician assistants) because of variation in billing practices (e.g. some bill under their own identifiers while others do not) that will confound outcome assessment. We will also exclude physicians who work at both trauma and non-trauma centers (because this limits the number of eligible patients they encounter), and those who work outside the continental US (because of differences in referral patterns).

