#### Hospitals:

We will obtain information about the organizational characteristics of each hospital at which physicians work using the 2022 Centers for Medicare and Medicaid Services (CMS) Healthcare Cost Report Information System (HCRIS). HCRIS contains facility-level characteristics of all non-federal hospitals, including geographic location (state, region), participation in a hospital network, total bed count, ICU bed count, ownership, and teaching status. Since HCRIS does not contain data on the trauma center status of hospitals, we will link HCRIS to the Trauma Information Exchange Program (TIEP) to identify the trauma center designation for each hospital in 2023.

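### The hospital-level sensitivity model in SAP 7.5 nests physicians within hospitals, but no rule ties a physician to one hospital; a physician seen at two would be counted as two independent units (minor; the primary model is not affected)

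*SAP*

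**What the plan says.** SAP 7.5 sets out the hospital-level structure as follows: "Random effects are included at the physician and hospital levels to account for clustering of patients within physicians and physicians within hospitals". It calls the clustering nested, uses random intercepts only, and on non-convergence says "we will remove the hospital-level random effect preferentially".

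The Version 1.4 deviation in the same section changes the primary model: "We decided to use unadjusted primary model with no baseline covariate adjustment and clustering only at the physician level". The hospital level stays as a sensitivity analysis of "clustering at the hospital level (patients nested within patients within hospitals), and then assessed variance to determine whether to retain the clustering or not". The Clustering row of SAP 10.1 agrees: physician only from Version 1.4, and physician-level in the manuscript.

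On where physicians work, the Protocol recruits "board-certified physicians who work exclusively in the EDs of non-trauma centers in the US" and collects "the organizational characteristics of each hospital at which physicians work". Its only multi-site rule is to "exclude physicians who work at both trauma and non-trauma centers". Under Research Activities (Patients), index patients are found by searching all claims filed under a trial physician's NPI, with no limit to one hospital. SAP 3.1.1 names a non-trauma center in the singular. Neither document says what to do with a physician who has index patients at two hospitals.

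**The concern.** Nesting physicians within hospitals is a true description only if each physician works at one hospital. The exclusion rule removes physicians who combine trauma and non-trauma sites and leaves in those who cover several non-trauma EDs. Recruitment runs through three staffing groups that together staff at least 600 EDs, so such physicians are possible.

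In a nested fit the physician intercept exists only within a hospital. One physician seen at two hospitals then becomes two physician-level units whose outcomes are linked by nothing. The physician is the unit of randomization, so the model drops correlation within the randomized unit and credits the trial with more information than it has. The purpose of this model is to check robustness to clustering, and here its error would run towards false precision.

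**Working it through.** **Inputs from SAP 7.2.** Within-physician correlation 0.45; median 1-2 eligible patients per physician; 400 physicians per arm, of whom at least 75% (300) have an eligible patient.

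**Assumptions, not in the documents.** 300 hospitals; hospital correlation 0 or 0.05; a share f of physicians who divide their patients at random between two EDs.

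**The plan's own figure.** With effective n per arm = physicians × m / (1 + (m − 1) × 0.45), one-sided 0.05, 80% power and an assumed baseline of 60%:
- 400 × 2 / 1.45 = 551.7 per arm gives a detectable difference of 7.4%.
- 300 × 1 = 300 per arm gives 10.1%.

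The stated 7.4-10% is therefore plausible with 0.45 as a per-physician correlation. It cannot be verified, because the power section gives no baseline. It does not depend on the hospital level.

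**One physician by hand.** Take two patients, one at each of two hospitals. In units of the patient-level variance, the true variance of their mean is (1 + 0.45)/2 = 0.725. The nested model takes it as 1/2 = 0.5. For that physician the assumed SE is √(0.5/0.725) = 0.83 of the true one. Physicians with one patient cannot be split, so the effect on the whole trial is much smaller.

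**Whole trial, linear approximation, 600 analysed physicians.**
- True covariance V: ρ_P = 0.45 for any two patients of the same physician, plus ρ_H for the same hospital.
- Nested working covariance W: ρ_P only where physician and hospital both match, plus ρ_H for the same hospital.
- Model variance: B = (X′W⁻¹X)⁻¹. True variance of the same estimator: B X′W⁻¹ V W⁻¹X B.
- r = model SE / true SE for the treatment term. Two-sided type I error = 2[1 − Φ(1.96 r)].

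Results for the nested model with ρ_H = 0:

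| Mean patients | Two-ED share f | Physicians actually split | r | Type I error |
|---|---|---|---|---|
| 1.5 | 0% | 0% | 1.00 | 5.0% |
| 1.5 | 25% | 5.0% | 0.979 | 5.5% |
| 1.5 | 50% | 10.8% | 0.959 | 6.0% |
| 1.5 | 100% | 21.6% | 0.925 | 7.0% |
| 2 | 25% | 9.6% | 0.963 | 5.9% |
| 2 | 50% | 19.1% | 0.933 | 6.7% |
| 2 | 100% | 37.7% | 0.886 | 8.3% |

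With ρ_H = 0.05, r at f = 25% and 50% is 0.976 and 0.958 (mean 1.5), and 0.956 and 0.929 (mean 2). A skewed count with mean 3 and median 2 gives 0.940 and 0.897 at the same shares with ρ_H = 0.

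**Physician-only model (the current primary).** r = 1.00 at every f when ρ_H = 0. With ρ_H = 0.05 and f up to 50% it is 0.984-0.993 at means 1.5 and 2. That small loss comes from leaving hospital out and is there even when f = 0, so it is not this mechanism.

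**Logistic cross-check.** 700 null trials per scenario, 800 physicians, patients of two-site physicians split evenly, one intercept per physician against one per physician-hospital pair.
- Mean 2, 80% under-triage: type I error 6.1% (f = 30%) and 7.0% (f = 50%), against 5.0-5.1% with one intercept per physician. Median |z| is inflated by 5% and 10%.
- Mean 1.39, 65% under-triage, f = 50%: |z| inflated by about 5%, equivalent to r ≈ 1/1.05 = 0.95.

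Monte Carlo SE near 5% is √(0.05 × 0.95/700) = 0.8 points, so 6.1% alone is weak. Direction and order of size agree with the table. Even splitting separates patients more than random splitting, and these fits have no hospital intercept.

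**The case against.** The strongest reply is that the quoted nesting sentence has been overtaken. Version 1.4 makes physician-only clustering primary, SAP 10.1 shows the manuscript model as physician-level, and the hospital effect is the first to go on non-convergence. This stands. A reader might infer that the primary standard error is too small because physicians are counted several times. The documents do not support that: the primary model already has one intercept per physician across all hospitals.

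A reader might also infer that hospital clustering was retained and that a reported result is affected. Nothing shows retention, and the appendix points the other way.

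Second, the singular in SAP 3.1.1 can be read as one hospital per physician, and the Protocol's plurals have plural subjects. Staffing groups being multi-site does not make each physician multi-site. This stands as far as it goes: multi-site work is allowed, not shown. The singular is still not a one-hospital rule, and claims are attributed without one.

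Third, the deviation note does not give the fitted structure: its nesting phrase repeats patients where physicians is presumably meant, and no level syntax is stated. That is a reason to specify the model.

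It is also tempting to say that physician variance would be misallocated in the retain-or-drop comparison. No calculation here tests that, and the point does not rely on it.

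**Conclusion.** Minor, and confined to the hospital-level sensitivity model. If some physicians have index patients at two or more hospitals and the model is fitted as nested, its treatment SE is understated by roughly 2-5% at a mean of 1.4-1.5 patients per physician and 4-7% at a mean of 2, with 25-50% of physicians at two sites. Two-sided type I error is then about 5.5-7%. The two-site share, hospital count and hospital correlation are assumptions, and the main figures come from a linear approximation with random splitting; even splitting gives somewhat more. If no physician has index patients at more than one hospital, the problem vanishes.

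**What to change.** In SAP 7.5, define the hospital-level sensitivity model with one intercept per physician across all hospitals, in one of two ways:
- enter hospital as an effect crossed with physician; or
- assign each physician to the hospital holding most of their index ED claims, so that nesting is true.

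If the crossed model can be fitted only by a Laplace approximation, do not rely on it alone, because clusters of one or two binary outcomes are very small. Report the modal-hospital fit beside it.

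Base the decision on whether to keep hospital clustering on that model. Report the number of physicians with index patients at more than one hospital; if it is zero, one sentence closes the matter. Correct the nesting phrase in the Version 1.4 note.

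The cost is SAP wording, one count from claims already held, and one re-run. The crossed model is slower, and the modal-hospital version ignores a physician's minority sites.
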